### **13.2. Sample Size/Accrual Rate**

Stage 1 will require 7 patients, with no further accrual if 0 of 7 respond. If  $> 1/7$  patients respond, accrual will continue until 21 patients have been enrolled. If  $> 3/21$  patients respond, this combination will be considered of sufficient activity, while 1-2 of 21 with benefit would be insufficient.

Patients of both genders, from all racial and ethnic groups are eligible for this trial if they meet the criteria outlined in Section 3.1. To date, there is no clinical information that suggests differences in selumetinib or sirolimus metabolism, disposition or disease response among racial or ethnic groups or between the genders, indicating that results of the trial will be applicable to all groups. Efforts will be made to extend the accrual to a representative population.

### **13.3. Analysis of primary endpoints**

The clinical benefit rate will be determined by identifying if patients have a PR, CR, or stable disease for 4 or more cycles. This total will be divided by the number of patients evaluable for response, and this fraction will be reported along with a 95% two-sided confidence interval.

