#### 11.1.1. Definitions

Evaluable for PET response: Patient must have FDG-PET performed at time points stated in protocol to be evaluable for PET response. PET response will be measured by PERCIST 1.0 (see section 11.1.6).

Evaluable for objective response: Any patient who is enrolled and receives at least one dose of selumetinib and one dose sirolimus will be considered evaluable for response provided: (1) the patient demonstrates progressive disease or death while on protocol therapy; or (2) the patient is observed on protocol therapy for at least one cycle and the tumor is not removed surgically prior to the time complete response or partial response is confirmed; or (3) the patient demonstrates a complete or partial response or stable disease as confirmed according to protocol criteria. The evaluation period for determination of best response will be 6 treatment cycles. All other patients will be considered non-responders.

Evaluable for toxicity: All patients who receive at least one dose of selumetinib or sirolimus and either experience a toxicity or complete the first cycle with no toxicity will be considered in the evaluation of toxicity.

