## **13. STATISTICAL CONSIDERATIONS**

### **13.1. Study Design/Endpoints**

The primary endpoint will be clinical benefit rate, which will be defined as a CR, PR, or stable disease  $\geq 4$  cycles. An evaluable patient will be classified as a responder (success) for the primary endpoint if the patient achieves a partial response (PR), complete response (CR), or stable disease (SD) at  $\geq 4$  cycles. The target clinical benefit rate will be 30% ( $p_1=0.30$ ), and a clinical benefit rate  $\leq 5\%$  ( $p_0=0.05$ ) will be considered uninteresting. Using a Simon's optimal two-stage phase II design with an  $\alpha=0.10$  (probability of accepting a poor treatment), and  $\beta=0.10$  (probability of rejecting a good treatment=0.10; power= 90%). Stage 1 will require 7 patients, with no further accrual if 0 of 7 respond. Since it may take several months to determine if a patient has responded, accrual may be temporarily paused while waiting to determine if there is at least one patient with a response among the 7 evaluable patients enrolled on stage 1. If  $\geq 1/7$  patients respond, accrual will continue until 21 patients have been enrolled. If  $\geq 3/21$  patients respond, this combination will be considered of sufficient activity, while 1-2 of 21 with benefit would be insufficient. Under the null hypothesis ( $p_0=0.05$ ), the expected sample size would be 11.2 patients, and the probability of early termination would be 69.8%.

Progression-Free Survival (PFS) is defined as the duration of time from the start of treatment to the time of objective progression or death.

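### The primary benefit rate is divided by evaluable patients in Section 13.3, while Section 11.1.1 counts the unevaluable as non-responders and Section 13.1 mixes evaluable with enrolled; the reported rate can only be held or raised

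*Combined protocol and SAP*

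**What the plan says.** Section 13.3 adds up the patients with CR, PR or stable disease for four or more cycles and continues: "This total will be divided by the number of patients evaluable for response". The fraction is reported with a two-sided 95% confidence interval.

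Section 11.1.1 requires at least one dose of each drug for a patient to be evaluable for objective response, plus one of three conditions:

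1. progression or death on protocol therapy;
2. in the plan's words, "the patient is observed on protocol therapy for at least one cycle and the tumor is not removed surgically" before CR or PR is confirmed;
3. CR, PR or stable disease confirmed under the protocol criteria.

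The paragraph ends: "All other patients will be considered non-responders".

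Section 13.1 sets the two-stage rule: "Stage 1 will require 7 patients, with no further accrual if 0 of 7 respond". It allows a pause while the team looks for a response "among the 7 evaluable patients enrolled on stage 1". If there is at least one, "accrual will continue until 21 patients have been enrolled", and 3 or more successes in 21 count as sufficient activity. The synopsis gives 21 as the maximum number of subjects. Sections 11.1.1, 13.1 and 13.3 contain no rule for replacing unevaluable patients.

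**The concern.** A non-responder belongs in the denominator as a failure. Section 11.1.1 puts the unevaluable patient there and Section 13.3 takes that patient out, so the same data give two different primary estimates. The exclusion is related to outcome: a patient who stops in cycle 1 for toxicity has had no opportunity to show four cycles of stable disease, and the first scheduled response scan is only before cycle 3 (Section 10.2). Removing such patients flatters the regimen.

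The same looseness reaches the interim rule. Stage 1 is described on evaluable patients and the end of stage 2 on enrolled patients, so the plan does not settle who makes up the 7 when one of them is unevaluable. At stake are the headline rate of a 21-patient trial and, at stage 1, whether accrual goes on.

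**Working it through.** **The design as stated (Section 13.1).** Inputs: p0 = 0.05, p1 = 0.30, 7 patients then 14 more, stop at 0 of 7, success at 3 or more of 21. Let X1 ~ Bin(7, p) and X2 ~ Bin(14, p).

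- Early termination under p0: 0.95^7 = 0.698. Expected size: 7 + 14 × (1 − 0.698) = 11.2. Both match the plan.
- P(success) = P(X1=1)·P(X2≥2) + P(X1=2)·P(X2≥1) + P(X1≥3).
- At p0: 0.2573 × 0.1530 + 0.0406 × 0.5123 + 0.0038 = 0.064, within the 0.10 that the plan allows for the "probability of accepting a poor treatment".
- At p1: 0.2471 × 0.9525 + 0.3177 × 0.9932 + 0.3529 = 0.904, against the stated 90%.

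**Who can be unevaluable.** Conditions 1 and 2 in Section 11.1.1 keep on-treatment progressors, on-treatment deaths and anyone observed for a full cycle. That leaves patients who leave in cycle 1 without progression or death on therapy (for example toxicity or refusal), patients who never took one of the two drugs, and patients whose tumor is resected before response is confirmed. Cycle 1 clinical deterioration is unclear: Section 5.5 lists clinical evidence under progressive disease, while Section 11.1.4 defines progression by measurements and lesions.

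**Effect on the reported rate.** With x successes and k unevaluable non-responders among 21, Section 13.3 gives x/(21 − k) and Section 11.1.1 gives x/21. The first is never smaller. The documents give no value for k, so it is assumed. For x = 3, with exact 95% intervals:

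| k (assumed) | Rate | 95% CI |
|---|---|---|
| 0 | 3/21 = 14.3% | 3.0% to 36.3% |
| 2 | 3/19 = 15.8% | 3.4% to 39.6% |
| 3 | 3/18 = 16.7% | 3.6% to 41.4% |
| 4 | 3/17 = 17.6% | 3.8% to 43.4% |

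**Effect on the final decision.** The rule is a count, so 3 successes pass under either denominator. Even if it were read as a proportion, 2/m ≥ 3/21 needs m ≤ 14, that is, 7 or more of 21 unevaluable.

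**Effect on the stage 1 stop.** Suppose one of the first 7 is unevaluable and the other six do not respond. Counted as one of the 7, that patient gives 0 of 7 and accrual stops. If 7 evaluable patients are required, one more is treated, and a success there opens stage 2. With one unevaluable patient and a 5% rate in the others, the chance of stopping is 0.95^6 = 0.735 on the first reading and 0.95^7 = 0.698 on the second.

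**Error rates with no replacement.** With three unevaluable in stage 2 (7 + 11 evaluable), alpha is 0.047 and power 0.883. With one in stage 1 and two in stage 2 (6 + 12), alpha is 0.044 and power 0.852. Here p0 and p1 apply to evaluable patients. Alpha falls in both cases.

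**Error rates with replacement to 7 and 21 evaluable.** Take a true 5% rate in all treated patients and let a share d (assumed) be unevaluable, all of them failures. The rate among evaluable patients is then 0.05/(1 − d).

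| d (assumed) | Rate among evaluable | Alpha |
|---|---|---|
| 5% | 5.3% | 0.072 |
| 10% | 5.6% | 0.082 |
| 15% | 5.9% | 0.093 |
| 20% | 6.25% | 0.107 |
| 30% | 7.1% | 0.143 |

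Alpha passes 0.10 at about d = 18%.

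**The case against.** The strongest reply is that this is a wording slip with little effect. Section 2.1.3 reports a median time to progression under 2 months with earlier targeted agents, so most early failures should be progressions, which stay in the denominator. Sections 6.1 and 6.2 allow holds of up to 21 days before removal, so some patients with cycle 1 toxicity would still reach a full cycle. A shift from 14.3% to 16.7% is small beside an interval from 3.0% to 36.3%. All of that stands and limits the size of the point. It does not reconcile the sections, because Section 13.3 uses the very term that Section 11.1.1 defines.

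Three stronger readings are tempting, and the documents do not support them:

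- *Early failures in general are dropped.* They are not; condition 1 keeps on-treatment progression and death.
- *The denominator costs power.* The fall to 0.883 or 0.852 comes from having patients who cannot respond. Counting the same patients as failures leaves the same 18 able to respond and the same threshold of 3, so the fix would not recover it.
- *The type I error is broken.* That needs replacement up to 21 evaluable, and no such rule is stated. Section 13.1 ends accrual at 21 enrolled; its mention of 7 evaluable patients is at most a hint of replacement in stage 1. Even with full replacement, alpha stays within 0.10 up to roughly 18% unevaluable, and the documents give no figure for that share.

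**Conclusion.** The inconsistency is real and concerns the primary analysis set. Followed as written, Section 13.3 removes patients whom Section 11.1.1 calls non-responders, so the reported rate can only be held or raised. Under an assumed 3 unevaluable patients and 3 successes, the difference is 2.4 percentage points (16.7% less 14.3%).

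The final go/no-go decision is not affected by the Section 13.3 denominator. The stage 1 stop could differ, because the plan does not say whether an unevaluable patient is one of the 7 or is replaced. The design figures reproduce, with alpha 0.064 and power 0.904, and a reader should not infer that the stated error rates fail under the plan as written.

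**What to change.** - **Section 13.3:** use as denominator every enrolled patient who received at least one dose of study drug, with unevaluable patients counted as non-responders, as Section 11.1.1 already states. Report the evaluable-only rate as a sensitivity analysis.
- **Section 13.1:** apply the 7 and the 21 to that same set and state that unevaluable patients are not replaced. Add a sentence on patients enrolled but never dosed, who fall outside the set.
- **Section 11.1.1:** keep the non-responder sentence and refer to it from Sections 13.1 and 13.3.

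With p0 and p1 read as rates among treated patients, this keeps alpha at 0.064, power at 0.904 and early termination at 69.8%. The cost is a few sentences, best settled before outcomes are known. The headline rate can only stay the same or fall slightly.

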### **13.4. Analysis of Secondary Endpoints**

Summary statistics will be used to describe the study population and baseline characteristics.

Progression free survival will be determined using the Kaplan-Meier method, with PFS at important time points (6 or 12 months for example) reported along with 95% two sided confidence intervals.

Toxicities to be summarized descriptively and tabulations on the type, severity, and relationship to study treatment will be performed.

Changes in FDG-PET avidity, tumor biomarkers, pain severity and pain interference ratings, and immune markers will be exploratory and summarized using descriptive statistics and when feasible compared using Wilcoxon rank test or pairwise t-test. Correlations to imaging response, toxicity, and immune markers will be made if feasible.

The comprehensive genomic analyses including next generation sequencing and ctDNA analysis will be performed in the Oncogenomics laboratory ([name]/NCI). Bioinformatics analysis will be primarily performed at the NCI using well-established pipelines previously developed.

### **13.5. Adverse event stopping rule**

If in the first 7 patients, 3 or more patients experience a grade 4 or higher non-hematologic adverse event, the study team will suspend accrual (if the trial is still accruing) and do a thorough analysis of the adverse events. If the grade 4 or higher events are felt to be at least possibly related to the study treatment, the study team, in consultation with SARC scientific leadership will make a recommendation to the sponsor to either alter the dose level of one or more of the drugs or to stop the trial due to toxicity. All participating IRBs will be notified of the adverse event and the recommendation.

At any point after 8 or more patients are enrolled, 1/3 or more of the patients experience a grade 4 or higher non-hematologic adverse event felt to be at least possibly related to the study treatment, the study team will suspend accrual to evaluate the adverse events. In consultation with the SARC scientific leadership, the study team will recommend that the trial continue without modification, alter the dose level of one or more of the drugs, or to stop the trial due to toxicity. The recommendation will be made to the sponsor and all participating IRBs will be notified of the adverse events and the recommendation.

Adverse events are reviewed on at least a monthly basis by the study team and the SARC Clinical Trial Review Committee and the trial will stop accrual if the adverse event stopping boundary is crossed.

#### **Adverse event stopping boundary summary:**

- Stop when 3 patients experience grade 4 or higher non-hematologic adverse event if total number of patients accrued is 7 or less
- Stop when 1/3 of the patients experience grade 4 or higher non-hematologic adverse event if the total number of patients accrued is 8 or more

## APPENDIX I: PERFORMANCE STATUS CRITERIA

PERFORMANCE STATUS CRITERIA			
Karnofsky and Lansky performance scores are intended to be multiples of 10			
Karnofsky		Lansky	
Score	Description	Score	Description
100	Normal, no complaints, no evidence of disease	100	Fully active, normal.
90	Able to carry on normal activity, minor signs or symptoms of disease.	90	Minor restrictions in physically strenuous activity.
80	Normal activity with effort; some signs or symptoms of disease.	80	Active, but tires more quickly
70	Cares for self, unable to carry on normal activity or do active work.	70	Both greater restriction of and less time spent in play activity.
60	Required occasional assistance, but is able to care for most of his/her needs.	60	Up and around, but minimal active play; keeps busy with quieter activities.
50	Requires considerable assistance and frequent medical care.	50	Gets dressed, but lies around much of the day; no active play, able to participate in all quiet play and activities.
40	Disabled, requires special care and assistance.	40	Mostly in bed; participates in quiet activities.
30	Severely disabled, hospitalization indicated. Death not imminent.	30	In bed; needs assistance even for quiet play.
20	Very sick, hospitalization indicated. Death not imminent.	20	Often sleeping; play entirely limited to very passive activities.
10	Moribund, fatal processes progressing rapidly.	10	No play; does not get out of bed.

Patients >16 years old: use Karnofsky performance criteria

Patients ≤ 16 years old: use Lansky performance criteria

## APPENDIX II: Restricted CYP and transporter co-medications

Cytochrome P450 and transporter inhibitor/inducer restrictions		
CYP/Transporter Category	Drugs	Minimum drug wash-out period
CYP3A4/5 Strong competitive inhibitors	Grapefruit juice, indinavir, itraconazole, ketoconazole, nefazodone, nelfinavir, saquinovir, telithromycin and troleandomycin and voriconazole	1 week
	Idelalisib	2 weeks
CYP3A4/5 Strong time dependent inhibitors	Bocepravir, clarithromycin, cobicistat, danoprevir, elvitegravir, LCL161, lopinavir, mibefradil, posaconazole, ritonavir, telaprevir and tipranavir	2 weeks
CYP3A4/5 Strong inhibitors (classification unknown)	Conivaptan	1 week
CYP3A4/5 Moderate competitive inhibitors	Amprenavir, aprepitant, atazanavir, cimetidine, cyclosporine, fluconazole, imatinib and netupitant	1 week
CYP3A4/5 Moderate time dependent inhibitors	ACT-178882, casopitant, crizotinib, darunavir, diltiazem erythromycin, ledipasvir, lomitapide, tofisopam and verapamil	2 weeks
	FK1706	half-life not found
CYP3A4/5 Moderate inhibitors (classification not known)	ciprofloxacin and dronedarone	1 week
	Schisandra Sphenanthera	half-life not found
CYP3A4/5 Strong Inducers	Carbamazepine, phenytoin, rifabutin, rifampicin and St. John's Wort	3 weeks
	Enzalutamide and phenobarbital	5 weeks
	Mitotane	114 weeks
	Avasimibe	half-life not found
CYP3A4/5 Moderate Inducers	Bosentan, genistein, lersivirine, lopinavir, modafinil, nafcillin, ritonavir, semagacestat, thioridazine and tipranavir	1 week

Cytochrome P450 and transporter inhibitor/inducer restrictions		
	Etravirine	2 weeks
	Efavirenz	3 weeks
	Talviraline	half-life not found
Pgp (MDR1) inhibitors	Dronedarone, erythromycin, indinavir, itraconazole, ketoconazole, lapatinib, lopinavir, ritonavir, quinidine and verapamil	1 week
	Vorapaxer	10 weeks
	Valspodar (PSC 833)	half-life not found
Pgp (MDR1) inducer	carbamazepine and rifampin	3 weeks
BRCP inhibitors	Atazanavir, cyclosporine, lopinavir, ritonavir, and tipranavir	1 week

Transporter Substrate Restrictions	
Transporters	Substrates
OATP (1B1 or 3)	Bosentan, fexofenadine, glyburide, pitavastatin, pravastatin, repaglinide , rosuvastatin
MATE(1 or 2K)	Cisplatin
Substrates in bold type have a narrow therapeutic index. Reference: Expert Opin Drug Metab Toxicol (2013) 9(6): 737-751. Washout periods should be 5x reported terminal half-lives.
